#### 4.1.5.3 Dose modifications for hypertension

An increased incidence of hypertension was observed in Sorafenib-treated patients. Hypertension was usually mild to moderate, occurred early in the course of treatment, and was amenable to management with standard antihypertensive therapy. Blood pressure should be monitored regularly and treated, if required, in accordance with standard medical practice. In cases of severe or persistent hypertension, or hypertensive crisis despite adequate antihypertensive therapy, permanent discontinuation of Sorafenib/ Placebo should be considered. In general, hypertension should be treated according to Table 7.

Management of treatment-emergent hypertension	
Grade of Event (CTCAE v3)	Management / next dose
Grade 1: asymptomatic and transient	Consider increased BP monitoring
Grade 2: asymptomatic and diastolic BP < 110 mmHg	Begin anti-hypertensive therapy and continue Sorafenib/ Placebo
Grade 2: symptomatic / persistent OR Diastolic BP ≥ 110 mmHg OR Grade 3	Sorafenib/ Placebo should be stopped* until symptoms resolve and diastolic BP returns to ≤ 100 mmHg. Treat subject with anti-hypertensives. When Sorafenib/ Placebo is re-started, reduce to 400 mg p.o. QD and possibly re-escalate dose later at the discretion of treating physician. If diastolic BP is not controlled to ≤ 100 mmHg on therapy, reduce Sorafenib/ Placebo to 400 mg p.o. every other day (QOD) and monitor BP closely If BP is not controlled on Sorafenib/ Placebo 400 mg p.o. QOD, study treatment should be discontinued
Grade 4: life-threatening	Discontinue Sorafenib/ Placebo permanently (end of study)
Please note the distinction between asymptomatic and symptomatic grade 2 hypertension. * Subjects requiring a delay of > 28 days should go off protocol therapy (end of study).	

*Table 7: Suggested dose modifications for Sorafenib/ Placebo-associated hypertension*

#### **4.1.5.4 Dose modifications for surgery**

Temporary interruption of Sorafenib/ Placebo is recommended in patients undergoing major surgical procedures. In advance of elective procedures, it is recommended that Sorafenib/ Placebo is interrupted for 5-7 days. There is limited clinical experience regarding the timing of re-initiation of Sorafenib/ Placebo therapy following major surgical intervention. Therefore, the decision to resume Sorafenib/ Placebo therapy following a major surgical intervention should be based on clinical judgment of adequate wound healing.

#### **4.1.6 Drug accountability**

Packaging, labeling and distribution will be performed by the Dresden pharmacy (Klinikapotheke des Universitätsklinikums Dresden) on behalf of the sponsor.

The drug will be distributed to the center pharmacies or to the responsible investigator in the center in plastic bottles containing an approximately 1 month drug supply (140 tablets of 200 mg Sorafenib each or Placebo), labeled according to the scheme described above (see chapter 3.3.1). The centers will be supplied with 18 bottles of medication for the initial treatment of 6 patients (3 x 3 bottles for treatment arm A and 3 x 3 bottles for treatment arm B) immediately after initiation. Three bottles contain 420 tablets (140 tablets per bottle) and are sufficient for a minimum treatment with study medication of 105 days, i.e. covering at least the first two courses of induction therapy and the first and second course of consolidation depending on daily dose and time interval between consolidations (see chapter 4.3).

The delivery of the initial three bottles per patient will be part of the starter kit and new starter kits will be organized by the Studienzentrale SAL when needed. Each local center is responsible for ordering more supply for each patient after use of the first three bottles. Each center will have to reorder when the patient starts to use the first tablets from the last remaining bottle. The reorder has to be done via the Studienzentrale SAL. Here the order will be documented and the pharmacy will be informed immediately.

With the first re-order (Erste Nachbestellung), the pharmacy will send 5 bottles sufficient for a minimum of 175 days, i.e. covering at least 5.5 months of maintenance therapy (maintenance therapy starts at day 8 of the third course of consolidation).

With the second re-order (Zweite Nachbestellung), the pharmacy will send 6 bottles sufficient for a minimum of 210 days, i.e. covering the remaining 6.5 months of maintenance therapy.

Each center has to document in a list, when which drug was given to whom. This list has to contain the date, the patient number, the batch number, the use-by date and the number of tablets dispensed. All empty medication bottles and left-over tablets have to be returned to the center investigator by the patients and have to be stored by the center investigator for documentation. The number of bottles and tablets for each individual patient will be registered by the documentation assistant. Medication documentation will be checked during the monitoring visits and empty bottles and unused medication will be returned to the pharmacy of Universitätsklinikum Dresden for disposal.

## **4.2 Standard cytotoxic therapy**

### ***Cytarabine (AraC)***

Cytarabine belongs to the group of chemotherapeutic agents called antimetabolites. Although the mechanism of action is not completely understood, it appears that cytarabine acts through the inhibition of DNA polymerase. A limited, but significant, incorporation of cytarabine into both DNA and RNA has also been reported.

Cytarabine is not active orally. It may be given by intravenous infusion or injection, subcutaneously, or intrathecally. When large intravenous doses are given quickly, patients are frequently nauseated and may vomit for several hours post injection. This problem tends to be less severe when the drug is infused.

A cytarabine syndrome has been reported to occur in patients. It is characterized by fever, myalgia, bone pain, occasionally chest pain, maculopapular rash, conjunctivitis and malaise. It usually occurs 6-12 hours following drug administration. Corticosteroids have been shown to be beneficial in treating or preventing this syndrome. If the symptoms of the syndrome are deemed treatable, the use of corticosteroids should be considered as well as continuation of therapy with cytarabine.

Like other cytotoxic drugs, cytarabine may induce anemia, leukopenia, thrombocytopenia and hyperuricemia secondary to rapid lysis of neoplastic cells.

Acute pancreatitis has been reported to occur in patients being treated with cytarabine who have had prior treatment with L-asparaginase.

Severe and at times fatal CNS, GI and pulmonary toxicity has been reported following high dose schedules of cytarabine. These reactions include reversible corneal toxicity and hemorrhagic conjunctivitis, which may be prevented or diminished by prophylaxis with a local corticosteroid eye drop; cerebral and cerebellar dysfunction, including personality changes, somnolence and coma, usually reversible; severe gastrointestinal ulceration, pulmonary edema, liver damage with hyperbilirubinemia. Rarely, severe skin rash, leading to desquamation has been reported.

For full details of the drug information please refer to the "Fachinformationsverzeichnis Deutschland" in its latest version.

### ***Daunorubicin***

Daunorubicin has antimitotic and cytotoxic activity through a number of proposed mechanisms of action. It forms complexes with DNA by intercalation between base pairs. It inhibits topoisomerase II activity by stabilizing the DNA-topoisomerase II complex, preventing the religation portion of the ligation-religation reaction which topoisomerase II catalyzes. Single strand and double strand DNA breaks result. Daunorubicin may also inhibit polymerase activity, affect regulation of gene expression, and produce free radical damage to DNA.

Daunorubicin must be given into a rapidly flowing intravenous infusion. It must *never* be given by the intramuscular or subcutaneous route. Severe local tissue necrosis will occur if there is extravasation during administration.

Myocardial toxicity manifested in its most severe form by potentially fatal congestive heart failure may occur either during therapy or months to years after termination of therapy. The incidence of myocardial toxicity increases after a total cumulative dose exceeding 400 to 550 mg/m^2 in adults.

Severe myelosuppression occurs when used in therapeutic doses; this may lead to infection or hemorrhage.

Dosage should be reduced in patients with impaired hepatic or renal function.

Daunorubicin may transiently impart a red coloration to the urine after administration, and patients should be advised to expect this.

For full details of the drug information please refer to the "Fachinformationsverzeichnis Deutschland" in its latest version.

### 4.3 Treatment plan for study and control arm

#### 4.3.1 Study design and flow chart

This is a double-blind, Placebo-controlled trial. All patients randomized into the control arm (called Arm P for Placebo in this chapter for descriptive purposes only) will receive Placebo tablets after chemotherapy and during maintenance. All patients randomized into the interventional arm (called Arm V for Verum in this chapter for descriptive purposes only) will receive Sorafenib after chemotherapy and during maintenance. The principal treatment strategy is given in the accompanying Figure 2.

[figure not shown]

Figure 2: Flow chart of treatment plan for study and control arm; “P” stands for Placebo, “V” stands for Verum (Sorafenib)

## 4.3.2 Induction therapy

### 4.3.2.1 Arm P (Standard cytotoxic therapy plus Placebo)

AraC	100 mg/ m  / day	continuous infusion over 24 hours	days 1-7
Daunorubicin	60 mg/ m  / day	infusion over 2 hours	days 3, 4 and 5
Placebo		2 tablets twice a day	from day 10 continuously until day 19

Table 8: Standard induction therapy plus Placebo

Patients will receive an identical second course of induction therapy starting earliest day 22 if the blast count in the bone marrow at day 16 is reduced. If there is no reduction in the blast count at day 16 or if there is even evidence of increased blast counts the patient should receive an alternative second induction therapy based on a high dose AraC application (HAM).

Alternative induction therapy - HAM (in the case of insufficient response to induction therapy I)

AraC	3g/ m  / 12hrs	infusion of 3 g/m  over 3 hours BID every 12 hours	days 1, 2 and 3
Mitoxantrone	10 mg/ m  / day	60 minutes infusion	days 3, 4 and 5
Placebo	2 tablets	twice daily	from day 10 continuously until day 19

Table 9: Alternative induction therapy plus Placebo

It is allowed to postpone the second course if the patient has an uncontrolled infection or transitory contraindications against chemotherapy. The second course can be started once these problems have been resolved.

### 4.3.3 Consolidation therapy

#### 4.3.3.1 Consolidation therapy for LR patients as defined by cytogenetics and for IR patients without an HLA-identical sibling

All patients in CR/ CRi after induction therapy should receive three courses of HD-AraC consolidation therapy not earlier than one week after attaining CR/ CRi. If, in the opinion of the treating physician, the patient's condition does not allow for consolidation therapy, consolidation therapy can be postponed for up to 4 weeks after a CR/ CRi is reached. However, if the patient is not attaining CR/ CRi 5 weeks after the beginning of the second induction therapy course he/she should be classified as treatment failure (definition of event and EFS see chapter 7) and study treatment should be terminated .

Criteria for the beginning of each consolidation course: platelets > 70.000/μl and neutrophils > 1.000/μl.

#### **Arm P (Standard cytotoxic therapy plus Placebo)**

AraC	3g/ m  / 12hrs	infusion of 3 g/m  over 3 hours BID every 12 hours	days 1,3 and 5
Placebo		2 tablets twice a day	from day 8 continuously until 3 days before first day of next chemotherapy course

Table 12: Consolidation therapy plus Placebo

Each consolidation course will start at least 1 week after regeneration of peripheral blood counts (platelets ≥ 70.000/μl, neutrophils ≥ 1.000/μl), but not earlier than day 28 of the first cycle

### **Arm V (Standard cytotoxic therapy plus Sorafenib)**

AraC	3g/ m  / 12hrs	infusion of 3 g/ m  over 3 hours BID every 12 hours	days 1, 3 and 5
Sorafenib	800 mg/ day	2 tablets twice a day	from day 8 continuously until 3 days before first day of next chemotherapy course

Table 13: Consolidation therapy plus Sorafenib

Each consolidation course will start at least 1 week after regeneration of peripheral blood counts (platelets  $\geq$  70000/ $\mu$ l, neutrophils  $\geq$  1000/ $\mu$ l), but not earlier than day 28 of the first cycle

If there is no full regeneration of peripheral blood counts at day 35 after high dose cytosinarabinosid chemotherapy the study medication should be reduced according to Table 3. If more than 2 levels of dose reduction are required, the patient will be excluded from the study.

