##### 4.1.5.1 Dose modification for hematological toxicity

Hematological toxicities will be considered not relevant for dose modification during the period of chemotherapy and the expected subsequent myelosuppression. However, these criteria will apply after hematopoietic recovery from the last chemotherapy course during the subsequent maintenance therapy.

Toxicity	Grade 1	Grade 2	Grade 3*	Grade 4*
Hematologic	Continue at the same dose level.	Continue at the same dose level.	Withhold dose until toxicity is grade <2, then resume treatment at the same dose level. If patient experiences a second grade 3 toxicity, withhold dose until toxicity is grade <2, then reduce dose to 400 mg p.o. QD and resume treatment.	Withhold dose until toxicity is grade <2, then reduce dose to 400 mg p.o. QD and resume treatment, or discontinue at the discretion of the principal investigator after discussion with study sponsor (safety desk at SAL).

\*Patients who develop grade 3 leukopenia, or grade 3/ grade 4 lymphopenia may continue Sorafenib/ Placebo treatment without interruption at the discretion of the investigator.

Table 3: Dose modifications and delays for hematologic toxicities of Sorafenib/ Placebo

Table 4 summarizes the recommendations for dose delays and modifications for all non-hematologic adverse events, except for skin toxicities and hypertension, which will be detailed separately (Table 5, Table 6, Table 7). These recommendations pertain, if the adverse event is considered to be related to Sorafenib/ Placebo, but not to the chemotherapy.

Toxicity	Grade 1	Grade 2	Grade 3*	Grade 4*
Non-hematologic	Continue at the same dose level.	Continue at the same dose level.	Withhold dose until toxicity is grade <1, then resume treatment at the same dose level. If patient experiences a second grade 3 toxicity, withhold dose until toxicity is grade <1, then reduce dose to 400 mg p.o. QD and resume treatment.	Withhold dose until toxicity is grade <1, then reduce dose to 400 mg p.o. QD. and resume treatment, or discontinue at the discretion of the principal investigator after discussion with study sponsor.

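### Section 4.1.5.1 reserves the Table 3 dose rules for the time after recovery from the last chemotherapy course, but section 4.3.3.1 invokes Table 3 for unrecovered counts at day 35 between consolidation courses

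*Protocol*

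**What the plan says.** Two sections of the protocol govern study-drug dosing when blood counts are low.

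- **Section 4.1.5.1, scope.** It opens with a general exemption: "Hematological toxicities will be considered not relevant for dose modification during the period of chemotherapy and the expected subsequent myelosuppression". It then says when the rules start: "However, these criteria will apply after hematopoietic recovery from the last chemotherapy course during the subsequent maintenance therapy".
- **Table 3, in the same section.** Grades 1 and 2 continue at the same level. For a first grade 3 the cell reads: "Withhold dose until toxicity is grade <2, then resume treatment at the same dose level". A second grade 3 is withheld and then resumed at 400 mg QD. Grade 4 is withheld and then resumed at 400 mg QD, or discontinued.
- **Section 4.3.3.1, Arm V, text under Table 13.** If the counts are not back in full, the rule is that "at day 35 after high dose cytosinarabinosid chemotherapy the study medication should be reduced according to Table 3". The next sentence adds: "If more than 2 levels of dose reduction are required, the patient will be excluded from the study".
- **Section 4.3.3.1, Arm P, text under Table 12.** It carries the same condition for starting the next course as Arm V, but no day-35 rule.
- **Section 4.1.5, with Table 2.** There are three dose levels (400 mg BID, QD, QOD). A patient who would need less than the lowest level comes off study treatment.

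**The concern.** Section 4.3.3.1 applies Table 3 to the very patients whom section 4.1.5.1 places outside it: those not yet recovered, with further chemotherapy possibly still to come. An investigator can defend leaving the dose alone from one section and acting under Table 3 from the other.

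Three things are at stake. The first is safety in cytopenic patients, since section 1.3.2 reports that myelosuppression with Sorafenib was seen mainly in combination with cytotoxic agents. The second is consistency of exposure: sites could give different amounts of study drug in consolidation while each follows the protocol. The third is retention. Section 3.4 requires withdrawal after an interruption of more than 28 consecutive days, so the reading chosen can decide whether a slowly recovering patient stays in the trial. Section 3.4 also speaks of analysing data documented up to the date of withdrawal, so it matters whether a patient leaves the study or only the study drug.

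**Working it through.** There is no stated figure to reproduce. The check sets the texts side by side for one patient: counts not regenerated at day 35 after the first or second high-dose AraC course.

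1. **Is the patient on study drug?** Table 13 gives it from day 8 until 3 days before the next course. The next course starts at least one week after counts regenerate. Without regeneration no next course can have been scheduled, so by default the patient is still taking study drug.

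2. **Does Table 3 apply?** The second sentence of section 4.1.5.1 sets two conditions: recovery from the last chemotherapy course, and the maintenance phase. This patient meets neither. Section 4.3.3.1 nevertheless sends the patient to Table 3. These are two rival rules on scope.

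3. **Does the instruction to reduce match Table 3?**

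| Situation in Table 3 | Table 3 action | Is it a reduction? |
|---|---|---|
| Grade 1 | same level | no |
| Grade 2 | same level | no |
| First grade 3 | withhold, resume at same level | no |
| Second grade 3 | withhold, then 400 mg QD | yes, after withholding |
| Grade 4 | withhold, then 400 mg QD or discontinue | yes, after withholding, or stop |

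 A reduction appears in two of the five situations, and there only after the drug has been withheld. In the other three, reducing according to Table 3 has no content. The table's footnote also lets some grade 3 leukopenia and grade 3 or 4 lymphopenia continue without interruption.

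4. **How many reduction levels?** Table 2 runs BID to QD to QOD, which is two reductions. A third would go below QOD. The limit of two in section 4.3.3.1 therefore agrees with Table 2, although the sentence cites only Table 3, whose cells name only the step to QD.

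5. **Is the consequence the same?** No. Section 4.3.3.1 excludes the patient from the study; section 4.1.5 ends study treatment.

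6. **Do both arms have the rule?** It is written under Arm V and not under Arm P. A blinded investigator cannot apply an arm-specific rule.

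7. **What counts as regeneration?** The sentence just before the day-35 rule uses platelets of at least 70,000/μl and neutrophils of at least 1,000/μl. The day-35 sentence adds the word full without saying whether it means the same values.

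**The case against.** The best defence is that section 4.1.5.1 exempts only the expected myelosuppression. Table 14 sets day 35 from the start of each consolidation course as the latest post-remission control, so failure to recover by then could be called unexpected and the day-35 rule a deliberate exception. This reconciles the first sentence of section 4.1.5.1. It does not reconcile the second, which asks for recovery from the last course and for maintenance. Nor does the protocol say that day 35 marks the end of expected myelosuppression. The study-specific exceptions in section 6.1 use day 40 from the start of the last cytotoxic therapy, though for SAE reporting. The day-35 sentence does not say whether it counts from the start or the end of the course. Counted from the last AraC day (day 5), it would be course day 40.

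It can also be said that the rule refers to study medication, closes the section, and so was meant for both arms. That is plausible, but the text should say so.

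Several stronger readings are tempting and are not supported:

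- **Three separate instructions.** Section 4.3.3.1 says to reduce according to Table 3, so it does not stand as an order independent of the table. There are two rival rules and a wording mismatch.
- **An exclusion trigger that can never be reached.** Read with Table 2, it can be.
- **No threshold for regeneration at all.** The preceding sentence supplies one. The higher platelet value in the CR definition (over 100,000/μl) is a response criterion that this rule does not cite.
- **A further contradiction because maintenance starts on day 8 of the last course.** Section 4.1.5.1 already makes the rules wait for recovery in that period. Only the day-35 sentence could conflict with it.
- **A count of affected patients or of milligrams at issue.** The protocol gives no rate of delayed recovery on which to base one.

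**Conclusion.** The contradiction holds. Section 4.1.5.1 applies Table 3 after recovery from the last course, and section 4.3.3.1 applies it before recovery between courses. The instruction to reduce does not describe Table 3 at grades 1 and 2 or at a first grade 3. Placement under one arm only and the differing consequence are secondary defects in the same rule.

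The conclusion rests on the wording, plus one inference: that the rule applies after any consolidation course, because it stands in the consolidation section. The size is qualitative. The conflict reaches every patient with unrecovered counts at day 35 between courses, in a number the documents do not allow one to estimate. It should be corrected because it touches safety and exposure. It does not by itself invalidate the primary comparison. A reader might take exclusion from the study to mean removal from the analysis, but section 7.2 evaluates every randomized patient in the assigned arm.

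**What to change.** Reconcile sections 4.1.5, 4.1.5.1 and 4.3.3.1 (both arms):

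- State once, for both arms and in terms of study medication, whether Table 3 applies to unrecovered counts at day 35 between consolidation courses, and from which day the 35 days are counted.
- Make the action wording in section 4.3.3.1 agree with the cells of Table 3.
- Confirm whether full regeneration means the platelet and neutrophil values in the preceding sentence.
- Cite Table 2 where reduction levels are counted.
- Use one consequence throughout. If only study treatment ends, say that follow-up for EFS and OS continues.

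The clinical action itself is for the sponsor to decide. The cost is about one paragraph and one table row in an amendment. Table 14 already schedules weekly blood counts during consolidation, so no new data are needed.
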